9.5.4.3 Reporting of Events Associated with Special Situations

9.5.4.3.1 REPORTING OF ADVERSE EVENTS ASSOCIATED WITH STUDY DRUG OVERDOSE, MISUSE, ABUSE, OR MEDICATION ERROR

Adverse events associated with study drug overdose, misuse, abuse, and medication error refer to AEs associated with uses of the study drug outside of that specified by the protocol. Overdose, misuse, abuse, and medication error are defined as follows:

Overdose	Accidental or intentional use of the study drug in an amount higher than the protocol-defined dose
Misuse	Intentional and inappropriate use of study drug not in accordance with the protocol
Abuse	Sporadic or persistent intentional excessive use of study drug accompanied by harmful physical or psychological effects
Medication error	Any unintentional event that causes or leads to inappropriate study drug use or subject harm while the study drug is in the control of site personnel or the subject.

All AEs associated with overdose, misuse, abuse, or medication error should be captured on the Adverse Event CRF and also reported using the procedures detailed in Reporting of Serious Adverse Events ([Section 9.5.4.1](#)) even if the AEs do not meet serious criteria. Abuse is always to be captured as an AE. If the AE associated with an overdose, misuse, abuse, or medication error does not meet serious criteria, it must still be reported using the SAE form and in an expedited manner but should be noted as nonserious on the SAE form and the Adverse Event CRF.

9.5.4.3.2 REPORTING OF STUDY-SPECIFIC EVENTS

Not applicable.

9.5.4.4 Expedited Reporting

The sponsor must inform investigators or as regionally required, the head of the medical institution and regulatory authorities of reportable events, in compliance with applicable regulatory requirements, on an expedited basis (ie, within specific time frames). For this reason, it is imperative that sites provide complete SAE information in the manner described above.

9.5.4.5 Breaking the Blind

In the case of a medical emergency where the appropriate treatment of the subject requires knowledge of the study treatment given, the investigator may break the randomization code for an individual subject. In all such cases, the AE necessitating the emergency blind break will be handled as an SAE in accordance with the procedures indicated above. Any broken code will be clearly justified and documented. The medical monitor must be notified immediately of the blind break.

9.5.4.6 Regulatory Reporting of Adverse Events

Adverse events will be reported by the sponsor or a third party acting on behalf of the sponsor to regulatory authorities in compliance with local and regional law and established guidance. The format of these reports will be dictated by the local and regional requirements.

All studies that are conducted within any European country will comply with European Good Clinical Practice Directive 2005/28/EC and Clinical Trial Directive 2001/20/EC. All SUSARs will be reported, as required, to the competent authorities of all involved European member states.

9.5.5 Completion/Discontinuation of Subjects

For purposes of entering subject disposition in the eCRF, a subject will be considered to have completed the study per protocol after the End of Study visit has been completed. The subject may elect to discontinue the study at any time for any reason. Subjects who discontinue study drug prematurely at any time after randomization at Visit 3 (Study Baseline) will be encouraged to return to the site as soon as practicable (preferably within 7 days). These subjects will be encouraged to continue to complete all study assessments (excepting PK samples, which will not be taken), including the Sleep Diary, and to return for all subsequent clinic visits, without the administration of study medication.

Subjects who agree will undergo an EDD Visit, during which all assessments will be conducted that would be made at an ET visit (except the T-BWSQ). These subjects need not attend the next regularly scheduled visit if this falls within the visit window of the next visit. Subjects who discontinue early from study drug are considered on study as long as they return for their regularly scheduled visits.

Subjects who do not agree to this will undergo an ET Visit and an EOS Visit, as described in the Schedule of Procedures/Assessments (Table 3). (revised per Amendment 01)

Subjects who withdraw because of an AE should also undergo a urine drug test.

If the investigator or sponsor discontinues a subject from the study prematurely, the investigator will promptly explain to the subject involved that the study will be discontinued for that subject and will provide appropriate referral for medical treatment and other necessary measures for the subject. A subject who has ceased to return for visits will be followed up by mail, phone, or other means to gather information such as the reason for failure to return, the status of treatment compliance, the presence or absence of AEs, and clinical courses of signs and symptoms. This information will be recorded in the CRF.

Subjects who discontinue early from the study will be discontinued for 1 of these primary reasons: AE(s), lost to follow-up, subject choice, lack of therapeutic effect, or administrative/other. Discontinuations due to noncompliance with alcohol restrictions will be assigned to “administrative/other”. In addition to the primary reason, the subject may indicate 1 or more of secondary reasons for discontinuation. Study disposition information will be collected on the Subject Disposition CRF.

A subject removed from the study for any reason will not be replaced. In some circumstances, a subject who screen fails before the Run-In period may be rescreened following consultation with the Sponsor. Any such subject will be assigned a new subject identification number.

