9.5.2 Schedule of Procedures/Assessments

[Table 3](#) presents the Schedule of Procedures/Assessments for this study.

Table 3 Schedule of Procedures/Assessments
(revised per Amendments 01 and 03)

Phase	Prerandomization				Randomization																	
	Screening		Run-In ^a	Study Baseline	Treatment Period 1 ^a						Treatment Period 2 ^a						Follow-Up		ET/EDD ^b	UNS ^c		
Period	1	2a	2b	3a	3b	4 ^d	5 ^d	6 ^d	7 ^{d,e}	8 ^{d,e}	9 ^d	10 ^{d,e}	11 ^{d,e}	12 ^d	13 ^{d,e}	14 ^{d,e}	15 ^d		EOS 16			
Day	-35 to -17	-17 to -14 ^f	thru - 1	1																		
Month ^g	-	-				1	2	3	4	5	6	7	8	9	10	11	12	(Wk 52 to 54)	(End Wk 54)			
Procedures/ Assessments																						
Informed consent	X																					
Demographics	X																					
Inclusion/exclusion criteria ^h	X	X		X																		
Sleep Disorders Screening Battery ^j	X																					
Sleep, medical, and psychiatric history	X																					
Physical examination ⁱ	X			X		X	X	X			X			X			X		X	X	X	X
Height	X																					
Vital signs	X			X		X	X	X			X			X			X		X	X	X	X
Weight	X			X		X	X	X			X			X			X		X	X		
Insomnia Severity Index	X			X		X		X			X			X			X					
Fatigue Severity Scale	X			X		X		X			X			X			X					
Prior and concomitant medication(s)	←----->																					
Beck Depression Inventory - II	X																					
Beck Anxiety Inventory	X																					
12-lead ECG ^k	X			X		X ^l		X ^l			X ^l			X ^l			X ^l		X ^l			
Urine pregnancy test ^m		X		X		X	X	X			X			X			X		X	X		
Serum pregnancy test (β-hCG) ^m	X																					
Urine drug test ⁿ	X	X		X		X	X	X			X			X			X		X	X ⁿ	X ⁿ	
Serology (Hepatitis B and C) ^o	X																					
Clinical laboratory tests ^p	X			X		X		X			X			X			X		X	X	X	X
eC-SSRS	X			X		X		X			X			X			X		X	X		
Sleep diary ^q	←----->																					
Dispense study drug			X		X	X	X	X			X			X								
Retrieve unused study drug				X		X	X	X			X			X			X					
Study drug compliance ^r				X		X	X	X			X			X			X					
Randomization					X ^{a,s}						X ^a											
EQ-5D-3L	X			X		X		X			X			X			X					
WPAI-GH	X			X				X			X			X			X					

Table 3 Schedule of Procedures/Assessments
(revised per Amendments 01 and 03)

Phase	Prerandomization				Randomization																
	Screening		Run-In ^a	Study Baseline	Treatment Period 1 ^a						Treatment Period 2 ^a						Follow-Up		ET/EDD ^b	UNS ^c	
Visit ^d	1	2a	2b	3a	3b	4 ^d	5 ^d	6 ^d	7 ^{d,e}	8 ^{d,e}	9 ^d	10 ^{d,e}	11 ^{d,e}	12 ^d	13 ^{d,e}	14 ^{d,e}	15 ^d		EOS 16		

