Day	-35 to -17	-17 to -14 ^f	thru -1	1																	
Month ^g	-	-				1	2	3	4	5	6	7	8	9	10	11	12	(Wk 52 to 54)	(End Wk 54)		
Procedures/ Assessments																					
PGI-Insomnia						X		X			X			X			X				
T-BWSQ																			X		
Adverse events ¹	←----->																				
Lemborexant PK sampling (plasma) ^u						X		X			X			X			X			X ^v	X

Footnotes for Table 3 (revised per Amendments 01 and 03)

AE = adverse event; β -hCG = beta-human chorionic gonadotropin; ECG = electrocardiogram; eC-SSRS = electronic Columbia-Suicide Severity Rating Scale; EDD = Early Drug Discontinuation; EOS = End of Study; EQ-5D-3L = EuroQOL version 5D-3L; ET = early termination; PGI-Insomnia = Patient Global Impression - Insomnia; PK = pharmacokinetics; T-BWSQ = Tyrer Benzodiazepine Withdrawal Symptom Questionnaire; UNS = unscheduled, WPAI-GH = Work Productivity and Activity Impairment Questionnaire – General Health.

- a: Subjects will not be informed that placebo will be administered during the Run-In Period. They will also not be informed of the timing of the placebo-controlled period (Period 1) or the active-treatment (only) period (Period 2), and will not be informed of the timing of the 2nd randomization for subjects who received placebo during Period 1.
- b: These assessments will be conducted at EOS, ET and EDD (except the T-BWSQ, which will not be conducted at EDD). Subjects who discontinue study drug prematurely at any time after randomization at Visit 3 (Study Baseline) will be encouraged to return to the site as soon as practicable (preferably within 7 days). These subjects will be encouraged to continue to complete all study assessments (excepting PK samples, which will not be taken), including the Sleep Diary, and to return for all subsequent clinic visits, without the administration of study medication. Subjects who do not agree to this will undergo an ET Visit and an EOS Visit. Subjects who do agree to continue with study procedures without the administration of study drug will undergo an EDD Visit. (revised per Amendment 01) These subjects need not attend the next regularly scheduled visit if this falls within the visit window of the next visit. Subjects who discontinue early from study drug are considered on study as long as they return for their regularly scheduled visits.
- c: Assessments during an UNS to be performed at the discretion of the investigator.

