- d: Visits 4, 5, and 6 are to be conducted within ± 4 days of the schedule. Visits 7 through 15, and EOS to be done within ± 7 days of the schedule. (revised per Amendments 01 and 03)
- e: The site will telephone the subject to assess AEs, to record concomitant medications and to review the sleep diaries. If any AE is clinically significant and requires follow-up, a clinic visit should be arranged (Unscheduled Visit).
- f: The Run-In Period may start between Day -17 and Day -14 and must continue for approximately 14 consecutive days and a maximum of 17 days. (revised per Amendment 01)
- g: Defined as a calendar month.
- h: Inclusion and exclusion criteria to be evaluated at visits other than or in addition to Visit 1 are listed in [Appendix 2](#) (revised per Amendment 01).
- i: Sleep Disorders Screening Battery comprises: STOPBang, International Restless Legs Scale, and Epworth Sleepiness Scale. (revised per Amendments 01 and 03).
- j: A full physical examination will be carried out at Screening and EOS (ET at the discretion of the investigator) and will include a brief neurological examination. A brief physical examination will be carried out at other visits.
- k: The ECG should be repeated if an abnormality is observed.
- l: If subject has a normal ECG baseline reading, but during any visit thereafter the QT is measured as >450 ms, 3 consecutive ECGs separated by 5 to 10 minutes will be performed to confirm the abnormality.
- m: Female subjects of child-bearing only.
- n: Urine drug test to be conducted at Unscheduled Visits at the discretion of the investigator and at ET only for subjects who withdraw because of an Adverse Event.
- o: Viral screening for hepatitis B (HBsAg) and hepatitis C (HCV antibody IgG) will be conducted.
- p: Clinical laboratory tests include hematology, blood chemistry, and urinalysis.
- q: Subjects should complete the Sleep Diary, within 1 hour of waketime, each day throughout the study until EOS. Sleep diaries should be reviewed for eligibility: for the 7 consecutive days immediately before Visit 2, and for the Run-In Period at Visit 3. Thereafter, the Sleep Diary should be reviewed for completeness

-
- once a month. (revised per Amendment 03)
- r: Study drug compliance (tablet count) will be carried out at each clinic visit from Visit 3a through Visit 15. (revised per Amendments 01 and 03)

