3.7.2 Patient Global Impression (PGI) - Insomnia

The PGI-Insomnia questionnaire captures the global impression of the study medication's effect at each postbaseline time point. The PGI-Insomnia has 3 items related to study medication effect (helped/worsened sleep, decreased/increased time to fall asleep, and increased/decreased TST) on a 3-point scale (1=positive medication effect, 2=neutral medication effect, and 3=negative medication effect) and 1 item related to perceived appropriateness of study medication strength also on a 3-point scale (medication: 1=too strong, 2=just right, and 3=too weak).

Each item will be summarized separately as number and percentage of subjects for each time point (Month 1, Month 3 and Month 6). Furthermore, each item will be analyzed using chi-square test for Month 1, Month 3 and Month 6 on observed data only based on FAS with no imputation for missing values, and repeated for age subgroups. For this analysis, each item will be categorized as follows: "positive medication effect" versus others for the first 3 item; "just right" versus others for the last item). This will also be repeated for the 12-month LEM exposure (On-Treatment Safety Analysis Set) will be summarized by treatment group and duration of exposure.

The time point window presented in 8.2.3 will be used to determine the analysis visit.

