6.2.3 Visit Windowing

For the laboratory values, ECG, vital signs, weight, eC-SSRS, T-BWSQ, PGI-Insomnia, WPAI-GH and EQ-5D-3L, the following visit windowing rule in [Table 10](#) will be applied based on measurements from unscheduled visits and early termination visits to attain the measurement for analysis for the given scheduled visit.

Table 10 Windowing Rules for Safety Endpoints

Visit	Target Visit Day (in study days)	Visit Window (in study days)
Visit 4 (Month 1)	30	2 - 45
Visit 5 (Month 2)	60	46 - 75
Visit 6 (Month 3)	90	76 - 135
Visit 9 (Month 6)	180	136 – Prior to the date of first dose of Period 2 If subjects discontinue treatment, the visit window will be 136 – 187
Visit 12 (Month 9)	270	The date of first dose in Period 2 - 315 If subjects discontinue treatment, the visit window will be 188 – 315
Visit 15 (Month 12)	364	316 - 371
End of Study (EOS)	378	Nominal visit (ie., the visit captured in eCRF will be used)

In case of multiple assessments within the same visit window, the assessment closest to the target visit day will be used in data analyses; in the event of two assessments being equally close to the scheduled visit day, the latest assessment in time will be used.

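### Table 3 schedules no ISI, FSS, EQ-5D-3L, WPAI-GH or PGI-Insomnia at the ET/EDD visit, although an EDD visit may replace a visit that collects them and SAP 6.2.3 windows early-termination values of three of them

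*Protocol*

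**What the plan says.** **Schedule.** In Protocol Table 3 (section 9.5.2) the row "Insomnia Severity Index" is marked at Visits 1 and 3a and at Months 1, 3, 6, 9 and 12. FSS and EQ-5D-3L follow the same pattern. WPAI-GH is the same without Month 1. PGI-Insomnia is marked at Months 1, 3, 6, 9 and 12. None of the five has a mark after Month 12, so none is scheduled at EOS, ET/EDD or an unscheduled visit. Weight, eC-SSRS and the clinical laboratory tests are marked in the ET/EDD column.

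**Content of the EDD visit.** Protocol 9.5.5 defines it as a visit "during which all assessments will be conducted that would be made at an ET visit (except the T-BWSQ"). Footnote b of Table 3 agrees: "These assessments will be conducted at EOS, ET and EDD (except the T-BWSQ, which will not be conducted at EDD").

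**Replacement rule.** 9.5.5, footnote b and the Synopsis all carry the sentence "These subjects need not attend the next regularly scheduled visit if this falls within the visit window of the next visit". Nothing moves the replaced visit's questionnaires to the EDD visit. The same section encourages these subjects to complete all assessments other than PK sampling and to attend later clinic visits off drug.

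**SAP.** Section 6.2.3 lists PGI-Insomnia, WPAI-GH and EQ-5D-3L among the data to be windowed "based on measurements from unscheduled visits and early termination visits to attain the measurement for analysis for the given scheduled visit". ISI and FSS are not on that list, and section 6.1.3 covers only the Sleep Diary. ISI and FSS change at Months 1, 3 and 6 is analysed by MMRM under MAR without imputation (SAP 3.4.2.4). PGI-Insomnia is tested "on observed data only based on FAS with no imputation for missing values".

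**The concern.** The ET/EDD visit is the one clinic contact that the plan guarantees itself around the time a subject stops drug, and it omits every efficacy and health-outcome questionnaire. Three consequences follow.

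- A subject who stops drug close to Month 1, 3 or 6 can comply fully with the protocol, remain on study, and still have no questionnaire for that time point.
- A subject who leaves through ET gives no questionnaire after the last scheduled visit attended.
- The SAP names a data source for three instruments that the protocol does not schedule, and leaves two named secondary endpoints (ISI daytime functioning and FSS) with no rule for assigning an off-schedule value to a month.

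Lack of therapeutic effect and adverse events are among the listed reasons for discontinuation (Protocol 9.5.5). A value near the time of stopping is the kind of observation that makes MAR more credible for ISI and FSS, and PGI-Insomnia has no model to fall back on. Protocol 9.5.1.6 describes the PGI-Insomnia outcome as an impression at the end of treatment, which for an early stopper is the ET/EDD visit. Protocol 9.7.1.6 also intends to use data from subjects who have stopped drug whenever they are available, and the replacement rule works against that.

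**Working it through.** The plan states no figure on this point. Its only discontinuation scenario (Protocol 9.7.2, up to 50% at Month 6) is not split between ET and EDD, so no per-arm count can be derived. The check is a reading of the table and two day counts.

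**1. Reading Table 3.** The table comes from extracted text in which some rows carry an extra trailing field. All five questionnaire rows are blank in every field after Month 12, so the finding of 0 of 5 instruments at ET/EDD does not depend on column alignment.

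**2. How often an EDD visit could replace a questionnaire visit in Period 1.**
- Windows, footnote d of Table 3: "Visits 4, 5, and 6 are to be conducted within" 4 days either side (Months 1 and 3 are Visits 4 and 6); "Visits 7 through 15, and EOS to be done within" 7 days either side (Month 6 is Visit 9).
- Target days 30, 90 and 180, from SAP Table 10.
- Assumption: EDD dates are spread evenly over 180 days.
- Lower figure, counting only window days before the target: 4 + 4 + 7 = 15; 15/180 = 8.3%.
- Upper figure, counting the full windows: 9 + 9 + 15 = 33; 33/180 = 18.3%.
- WPAI-GH (Months 3 and 6 only): (4 + 7)/180 = 6.1% to (9 + 15)/180 = 13.3%.

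So about 82% to 92% of EDD dates would cost no scheduled questionnaire visit, and the rest would cost one.

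**3. How often a form at ET would add an analysable value.** SAP Table 10 assigns days 2-45 to Month 1, 46-75 to Month 2, 76-135 to Month 3, and day 136 onward to Month 6 (to day 187 for subjects who discontinue). The assessment closest to the target day is used. Assume scheduled visits fall on target days and ET dates are uniform over 180 days.

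| ET day | Assigned to | Result | Days gained |
|---|---|---|---|
| 2-29 | Month 1 | fills an empty cell | 28 |
| 31-45 | Month 1 | scheduled form is closer | 0 |
| 46-75 | Month 2 | no questionnaire endpoint | 0 |
| 76-89 | Month 3 | fills an empty cell | 14 |
| 91-135 | Month 3 | scheduled form is closer | 0 |
| 136-179 | Month 6 | fills an empty cell | 44 |

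Total: 28 + 14 + 44 = 86; 86/180 = 47.8%. For WPAI-GH: 14 + 44 = 58; 58/180 = 32.2% (58/178 = 32.6% if only days 2 to 179 are counted). For ISI and FSS the 48% applies only once they are placed under Table 10. The earliest value labelled Month 6 would be 180 - 136 = 44 days early.

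**The case against.** The strongest reply is that the plan already looks after these subjects. Those who stop drug but stay on study are asked to keep completing assessments and to attend later visits, and the replacement rule is a permission, not an instruction. This stands: an EDD subject loses at most one questionnaire visit through the rule. A reader might infer that these endpoints are lost whenever a subject stops; the documents support that only for the moment of stopping and for subjects who leave through ET.

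Second, SAP 6.2.3 is one generic rule for many data types. It also draws on unscheduled visits, where assessments are at the investigator's discretion, and it lists the T-BWSQ, which SAP 3.6.7.2 describes as completed at EOS only. Being listed therefore does not prove that collection at ET was intended. That is fair, although 9.5.5 and footnote b, by excepting the T-BWSQ at EDD alone, imply it is done at ET. Either way the two documents do not match for three instruments. The mismatch does not extend to ISI and FSS, whose gap is the absence of any window.

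Third, MMRM keeps the Month 1 and Month 3 ISI and FSS values of subjects who leave later, so the analysis does not rest only on those who stayed. This stands. A reader might infer that each arm's result will look better than it was. The documents do not support a direction: the effect on the between-arm difference depends on differential dropout, for which they give no figures.

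Fourth, adding forms at ET/EDD is partly a design preference, and the affected endpoints carry no multiplicity control. That limits the weight of the point but does not remove the inconsistency.

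**Conclusion.** The point holds as a gap in the schedule and a mismatch between protocol and SAP. Followed as written, the plan forgoes questionnaire data from some subjects still on study and from every subject at an ET visit. The affected endpoints are ISI and FSS (secondary; MMRM under MAR) and EQ-5D-3L, WPAI-GH and PGI-Insomnia (exploratory; the last on observed data only). The consequence is avoidable missing data with possible bias of unknown direction. The primary and key secondary endpoints come from the daily Sleep Diary and are unaffected.

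The size rests on uniform timing of stopping and, for the ET count, on scheduled visits falling on their target days. About 8% to 18% of Period 1 EDD dates could replace a questionnaire visit, and a form at ET would fill an otherwise empty cell on about 48% of days (about a third for WPAI-GH). A reader might count every subject who leaves through ET as a value the change would recover. That overstates the gain: on about half the days the form would be displaced by a closer scheduled one or fall in Month 2, and the endpoints are defined at Months 1, 3 and 6, not at end of treatment.

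**What to change.** 1. In Protocol Table 3, mark ISI, FSS, EQ-5D-3L, WPAI-GH and PGI-Insomnia in the ET/EDD column. At minimum, state in 9.5.5 and footnote b that an EDD visit replacing a scheduled visit includes that visit's questionnaires.
2. Add ISI and FSS to the list in SAP 6.2.3, so that they fall under the Table 10 windows.
3. If the sponsor prefers not to collect the forms at ET, remove early termination visits as a source for PGI-Insomnia, WPAI-GH and EQ-5D-3L in SAP 6.2.3, so that the two documents agree.

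The cost is a few marks in one column, a short addition to the SAP, and several brief self-report forms at a visit the subject already attends. One downside should be acknowledged in the SAP: some values windowed to Month 6 would be up to 44 days early.
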